## **5.3.** Treatment Assignment Procedures

#### **5.3.1.** Randomization Procedures

Per ICH E6: GCP, screening records will be kept at each site to document the reason why an individual was screened, but failed trial entry criteria. The reasons why individuals failed screening will be recorded in the Data Coordinating Center's (DCC's) AdvantageEDCSM (Electronic Data Capture) system.

Once consented and upon entry of demographic data and confirmation of eligibility for the trial, the subject will be enrolled. Enrollment of subjects will be done online using the enrollment module of AdvantageEDCSM. Subjects will be randomized 1:1 to receive oral therapy from Strategy 1 vs. Strategy 2. Subjects will be stratified by (1) pyelonephritis vs. other cUTIs and (2) participating site.

The list of randomized treatment assignments will be prepared by statisticians at the DCC (The Emmes Corporation) and included in the enrollment module of its Internet Data Entry System (IDES). IDES will assign each subject a treatment code and treatment assignment from the list after demographic and eligibility data have been entered.

Instructions for use of the enrollment module are included in the AdvantageEDCSM User's Guide. Manual back-up procedures and instructions are provided for use in case the site temporarily loses access to the Internet or the online enrollment system is unavailable.

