## 11.4. Final Analysis Plan

Planned analyses of all primary and secondary endpoints will be described in detail in the SAP to be prepared by the DCC and finalized prior to unblinding of the study data.

The primary analysis will be a superiority analysis of treatment success at TOC by study arm in the micro-ITT analysis population. Multiple imputation will be used in the case of missing values for treatment success at TOC in the micro-ITT population. The test of the null hypothesis of no difference between the strategies for the primary outcome (Section 11.1) will be performed using linear regression, and will include site, pyelonephritis, and number of bacterial species detected in the urine at baseline as covariates. Further details of the analysis, including the multiple imputation model, will be described thoroughly in the SAP. As a secondary analysis, a difference in treatment success at EOT by treatment strategy will be tested in the micro-ITT population, using methods analogous to the primary analysis. Sensitivity analyses will be performed for the primary analysis including a complete case analysis in which subjects are analyzed as randomized without imputation and tipping point analyses.

The safety analysis population will include all subjects receiving at least one dose of study drug. 95% confidence intervals of frequencies of solicited and unsolicited adverse events, SAEs and AESIs will be provided using the Wilson score method.

Frequency and number of solicited adverse events of grade 2 and above will be reported by treatment arm, study day, and severity, and differences between treatment arms in frequency of grade 2 and above severity solicited adverse events after the first dose of study drug will be tested using Fisher Exact Tests. For subjects receiving fosfomycin, frequency and number of each solicited adverse event of grade 2 and above severity occurring any time from date of first dose of fosfomycin in subjects receiving 2 or more doses until 2 days after last dose of fosfomycin will be tabulated.

Frequency and number of SAEs in subjects receiving at least two doses of fosfomycin during the trial will be tabulated.

For subjects receiving fosfomycin, frequency of each unsolicited adverse event of grade 2 and above severity occurring in subjects receiving at least two doses of fosfomycin until 2 days after last dose of fosfomycin will be tabulated overall and by MedDRA® System Organ Class and Preferred Term.

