Allison (2005) [1] showed that this approach can be extended to allow covariates in the model. Hence, Using simulation studies, Allison showed that multiple imputation using linear regression performed well in estimating regression coefficients in different missing data scenarios (MCAR, MAR) even when compared to logistic regression. The added benefit of using the linear regression model is that it directly provides proportion differences along with their 95% CI after applying PROC MIANALYZE to the model fits from the M multiply imputed datasets.

Due to the low sample size at the close of the study, the results of this hypothesis test should be interpreted with care since the required power to conclude a significant difference was not achieved. An estimate of the composite cure and composite cure difference between the two strategies along with its 95% Wald CI (no continuity correction) and p-value will be provided.

Details of multiple imputation methods for efficacy outcomes specific to DMID-15045 are described in Section 8.4.1.

Step 1: A multiple regression model: $Y_i = \beta_0 + \beta_1 X_1 + \beta_2 X_2 + \beta_3 X_3 + \dots + \beta_c X_c + \epsilon_i$, $\epsilon_i \sim N(0, \sigma^2)$ where Y_i represents the indicator for composite cure and X_c are the covariates described in Section 8.4.1 to be used in the multiple imputation model to generate M multiply imputed datasets.

Step 2: A simple linear regression model $Y_i = \beta_0 + \beta_1 trt + \epsilon_i$ will be fit on each of the m multiply imputed datasets. Estimates of composite cure from each of the m models will be given by the β_1 which represent the difference in treatment success between the two strategies.

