Step 3: The final composite cure will be obtained by combining M estimates of composite cure estimates using PROC MIANALYZE as described in Section 8.4.1. The p-value for trt from this step will be used for hypothesis testing. The null hypothesis will be rejected if the p-value is less than or equal to 0.05 and will conclude that the treatment success at TOC is conditional on treatment strategy. If the composite cure estimate for strategy 1 is above that of strategy 2 and the p-value is ≤ 0.05 , then we can conclude that strategy 1 is superior to strategy 2 at TOC. Similarly, if the composite cure estimate for strategy 2 is above that of strategy 1 and the p-value is ≤ 0.05 , then we can conclude that strategy 2 is superior to strategy 2 at TOC. If the null hypothesis is not rejected, we will conclude that evidence from the trial is insufficient to conclude that either strategy is superior.

The proportion of subjects with composite cure at TOC in each strategy will be provided. The difference in the proportion of subjects having composite cure at TOC between Strategy 1 and Strategy 2 along with the 95% Wald CI (no continuity correction) for the treatment difference from Step 3 above will be provided (Table 20). A listing of urine culture results used for calculating microbiological cure is provided in Listing 8. A listing of UTI signs and symptoms used for calculating clinical cure at TOC is provided in Listing 9.

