8.2. Secondary Efficacy Analyses

8.2.1. Analysis of Composite Cure at EOT in the Micro-ITT Population, Performed in an Analogous Manner to the Primary Analysis

The secondary efficacy endpoint is the difference in the proportion of subjects achieving treatment success at EOT between Strategy 1 and Strategy 2. The secondary efficacy analyses will also be performed for the micro-ITT population.

The null hypothesis corresponding to the secondary analysis of this study was:

H_0 : The probability of success at EOT is not conditional on the treatment strategy.

The secondary analysis will be conducted in a similar manner as the primary analysis by using multiple imputation with a linear regression model to impute missing values for treatment success at EOT in the micro-ITT population. Details of the multiple imputation methods are described in Section 8.1.1. and Section 8.4.1.

The proportion of subjects with composite cure at EOT in each strategy will be provided. The difference in the proportion of subjects having composite cure at EOT between Strategy 1 and Strategy 2 along with the 95% CI for the treatment success difference will be provided (Table 20). A listing of individual

microbiological response data at EOT is provided in [Listing 8](#) and a listing of UTI symptoms used for calculating clinical cure at EOT is provided in [Listing 9](#).

8.2.2. Sensitivity Analyses of Composite Cure at TOC and EOT in the Micro-ITT Population

A sensitivity analysis will be performed for the primary analysis using subjects in the micro-ITT population that have no missing treatment success values at TOC (CC-TOC Population) and EOT (CC-EOT Population). These subjects will be analyzed as randomized without imputation. The treatment success will be estimated from this model: $Y_i = \beta_0 + \beta_1 trt + \epsilon_i$

For this analysis, estimate of treatment success in each strategy, the difference in the proportion of subjects in this population having composite cure at TOC and EOT between Strategy 1 and Strategy 2 with the 95% Wald CI (no continuity correction), and p-value will be provided in [Table 21](#). Additionally, a sensitivity analysis of best/worst case scenarios using various percentages of missing composite cure is provided in [Table 24](#) for TOC and [Table 25](#) for EOT.

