8.4. Imputation of Missing Data

8.4.1. Multiple Imputation of Missing Values of Treatment Success at TOC and EOT

Primary and secondary analyses depend on multiple imputation of treatment success at TOC and EOT, respectively. First, a table showing the number and percentage of missing data for each outcome at EOT and TOC will be presented in [Table 18](#). In order to use the MI model to adjust for bias caused by missing data, we assume that data is missing at random (MAR). To test this assumption, we will fit a logistic model for missing data indicator D (1 if missing, 0 if non-missing) adjusting for covariates of the MI model listed below. Parameter estimates, 95% confidence intervals, and p-values from this model will be provided in

Table 19 at TOC and at EOT. If some of these covariates have a significant relationship with the missing data indicator ($p\text{-value} \leq 0.05$), then the MAR assumption is more likely than MCAR.

In case of missing treatment success at TOC or EOT, multiple imputations of missing treatment success at TOC or EOT will be performed independently, and each subject will have their missing endpoints imputed independently of other subjects' imputations using a subject-specific imputation model. The pseudocode shown below details how missing data for treatment success at TOC (or EOT) will be imputed using m multiply imputed datasets from linear models. The following covariates will be considered for the MI model: treatment strategy, site indicators, age, sex, pyelonephritis status, and number of bacterial species. The number of imputed, m , datasets will be chosen based on the average percent of missing data. Default value will be $m=20$ since sample size calculation assumed a 20% drop-out rate. Similar models will be fit for clinical cure and microbiological success.

As a first step to multiple imputation, an ordered list of variables to include in the subject-specific imputation model will be constructed. Ordering is specified so that exact imputation results from final data are prespecified may be replicated in SAS (using seeds described below). The complete ordered list of variables for the imputation models for treatment success, clinical cure, and microbiological success at TOC and EOT is below:

- Treatment Strategy (Strategy 2 is the reference)
- Indicator of subject enrolled at the site with the second most number of subjects enrolled (binary indicator)

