- Indicator of subject enrolled at the site with the third most number of subjects enrolled (binary indicator)
- Indicator of subject enrolled at the site with the fourth most number of subjects enrolled (binary indicator)
- Indicator of subject enrolled at the site with the least number of subjects enrolled (binary indicator)
 - Note: the site with the most number of subjects enrolled is reference for site. Language is written to allow for an arbitrary number of sites. In the event of a number of ties for the number of subjects enrolled, tied sites will be ordered in ascending alphanumeric order in the list of model variables.
- Age at enrollment
- Sex (Male is the reference)
- Indicator for pyelonephritis (No is the reference)
- Number of species detected in the urine at baseline (1 is the reference)

The actual list of MI model variables for each subject-specific imputation model will follow the ordering above but omit variables with missing values. The below pseudo-code / SAS code outlines the creation of 20 multiple imputation datasets. Note that the seeds used in the actual analysis must follow the specification given in the pseudo-code and subjects must be processed in the order described in the pseudo-code. Clinical cure and microbiological success will simultaneously be imputed with composite cure at each respective time point. The pseudo-code is in terms of TOC endpoints, but the general logic is also applicable to the EOT.

*Outcome variables: trtsuccess clincure microsuccess

DEFINE i=index variable for subjects having treatment success imputed.

Subjects requiring imputation are sorted in ascending order
by PATID.

DEFINE N=number of subjects requiring imputation

DEFINE g&i=analysis dataset containing predictors and treatment success for
CC-TOC subjects as well as subject i (only one subject not in
CC-TOC included). Note that CC-TOC subjects that are missing a value
for one or more variables in the subject-specific imputation model are excluded.

DEFINE imp_g&i = g&i, with 20 imputed values for the missing treatment success
added by PROC MI

DEFINE &&modelVars_&i = list of observed variables in subject i (site1, site2, site3, site4, age, sex,
treatment strategy, pyelonephritis, Nbacterias), to be used for imputation of treatment success, clinical cure,
and microbiological cure.

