Step 1: Imputation model: This model will generate 20 datasets with each dataset containing original complete data along with imputed values for subjects with missing endpoint.

```
%do i=1 %to &N;
```

```
PROC MI data= g&i out= imp_g&i seed= 22131&i NIMPUTE=20 noprint;
  Var &&modelVars_&i trtsuccess_TOC clincure_TOC microsuccess_TOC;
  monotone regression(trtsuccess_TOC = &&modelVars_&i);
  monotone regression(clincure_TOC = &&modelVars_&i);
  monotone regression(microsuccess_TOC = &&modelVars_&i);
```

```
run;
```

```
%end;
```

imp_g&i will be subset to contain only rows for the subjects with imputed treatment success, clinical cure,
and microbiological success and merged together and with CC-TOC data to create the twenty complete
multiply imputed datasets

Step 2: Analysis model: This model will fit regression models to the 20 complete datasets to obtain parameter estimates for treatment success, clinical cure, microbiological success.

```
proc reg data= imp_g outest= out_trts covout noprint;
```

```
model trtsuccess= trt /clb alpha=0.05;
```

```
by _imputation_;
```

```
run;
```

```
proc reg data= impdata outest= out_clinc covout noprint;
model clincure= trt /clb alpha=0.05;
by _imputation_;
run;

proc reg data= impdata outest= out_micros covout noprint;
model microsucceed= trt/clb alpha=0.05;
by _imputation_;
run;
```

Step 3: Combine estimates from models in step 2 to obtain overall estimates summarized over 20 imputed datasets;

```
proc mianalyze data= out_trts alpha = 0.05;
modeleffects trt;
ods output ParameterEstimates=parms_trts;
run;

proc mianalyze data= out_clinc alpha = 0.05;
modeleffects trt;
ods output ParameterEstimates=parms_clinc;
run;

proc mianalyze data= out_micros alpha = 0.05;
modeleffects trt;
ods output ParameterEstimates=parms_micros;
run;
```

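### The SAP drops the protocol's covariates from the efficacy model, keeps them only for imputation, and does not record the change

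*SAP*

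**What the plan says.** **Protocol.** Section 11.4 specifies linear regression for the primary null hypothesis and says the model "will include site, pyelonephritis, and number of bacterial species detected in the urine at baseline as covariates". EOT is to be analysed by analogous methods. Section 5.3.1 gives the strata: "Subjects will be stratified by (1) pyelonephritis vs. other cUTIs and (2) participating site".

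**SAP analysis model.** Section 8.1.1 Step 2 is "A simple linear regression model" with treatment as its only term. The code in 8.4.1 is "model trtsuccess= trt /clb alpha=0.05", with matching statements for clinical cure and microbiological success. Step 3 pools these fits: "The p-value for trt from this step will be used for hypothesis testing". EOT (8.2.1) follows the same steps. For the complete-case analysis in 8.2.2, "The treatment success will be estimated from this model", and that model again has an intercept and treatment only.

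**Where the covariates went.** Section 8.4.1 says: "The following covariates will be considered for the MI model: treatment strategy, site indicators, age, sex, pyelonephritis status, and number of bacterial species". They therefore enter the imputation of missing outcomes, with age and sex added, and the logistic missingness model of Table 19.

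**What is disclosed.** The Preface says in general terms that the analyses were updated for the smaller sample. Section 6.7 says sites are pooled in the primary analysis. Section 6.4, on covariates and subgroups, names the strata but no analysis-model covariates. Section 12 lists four changes: no interim analysis, heteroresistance analyses removed, relapse analysis removed, and an ITT population added.

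**The concern.** The two documents define different primary tests, and the SAP's own list of changes does not say so. Having the covariates in the imputation model is no substitute. That model shapes only the imputed values; subjects with observed outcomes are still compared without adjustment, and with nothing missing the covariates would play no part.

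Two of the three covariates are randomisation strata. Stratifying removes between-stratum variation from the true sampling variance of the treatment difference, but a treatment-only regression leaves it in the residual variance. If the strata are prognostic, the interval is too wide and the test conservative. At stake are a correctly sized interval for the primary estimate and a traceable route from protocol to analysis. Bias is not at stake.

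**Working it through.** **The plan's own power figures.** Inputs from SAP Section 5: 80% v 70%, two-sided 5% z-test, no continuity correction. Power ≈ Φ[(0.10 − 1.96·SE0)/SE1], with SE0 = √(2·0.75·0.25/n) and SE1 = √((0.8·0.2 + 0.7·0.3)/n).

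- Planned: 634 × 0.92 / 2 = 291.6, so n = 291 per arm. SE0 = 0.0359, SE1 = 0.0357, power = 79.7%, or 79.4% to 80.0% allowing for the interim look. Stated: 80%.
- Actual: n = 24 per arm (even split of 48 assumed). SE0 = 0.1250, SE1 = 0.1242, power = Φ(−1.168) = 12.1%, or 12.4% counting both tails. Stated: 12%.

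Both reproduce, and both describe an unadjusted test.

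**Rough size of the standard-error excess.** Assume 70% mean success, 60% pyelonephritis and a 20-point gap between strata. Outcome variance is 0.7 × 0.3 = 0.21. Between-stratum variance is 0.6 × 0.4 × 0.20² = 0.0096, which is 4.6% of the total. With perfect balance the treatment-only SE is too large by a factor 1/√(1 − 0.046) = 1.024, about 2%. With no gap it is 0%.

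**Simulation.** The documents do not say how prognostic the strata are, so these inputs are assumptions: permuted blocks of 4 within 5 sites × pyelonephritis, 62 randomised with 48 kept at random, site shares 40/25/15/12/8%, 60% pyelonephritis, 70% mean success, 12% with more than one species, no pooling of sites. The missing-data runs set 20% missing completely at random and use SAP-style per-subject normal imputation with M = 20. There were 20,004 trials per cell with nothing missing and 12,004 with 20% missing. Each cell reads treatment only / plus pyelonephritis / full Protocol 11.4 set.

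| Assumed stratum effect | Type I error, none missing (%) | Type I error, 20% missing (%) | Power at 10 points, none missing (%) |
|---|---|---|---|
| None | 5.2 / 5.0 / 5.0 | 5.2 / 5.3 / 5.8 | 11.9 / 11.5 / 10.9 |
| 20-point pyelonephritis gap | 4.8 / 5.0 / 5.0 | 4.7 / 5.0 / 5.5 | 11.4 / 11.7 / 11.3 |
| 30-point gap + 20-point site spread | 4.3 / 4.8 / 5.1 | 4.2 / 5.0 / 5.5 | 10.6 / 11.9 / 11.7 |

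Monte Carlo error is about 0.15 to 0.2 points for type I error and 0.2 to 0.3 for power.

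Mean treatment-only SE against true SD (null, nothing missing):
- no effect: 0.1326 / 0.1325, excess 0%
- 20-point gap: 0.1325 / 0.1298, excess 2%
- 30 + 20 points: 0.1326 / 0.1270, excess 4%

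Change in true SD against treatment only, same three scenarios:
- plus pyelonephritis: 0.1330, 0.1292, 0.1251, that is +0.4%, −0.5%, −1.5%
- full set: 0.1372, 0.1331, 0.1291, that is +3.5%, +2.5%, +1.7%

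One stratum term therefore costs almost nothing and helps if prognostic. The full set enlarges the true SD in all three scenarios.

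**Second simulation, other assumptions.** With 50% pyelonephritis, site shares 35/25/20/12/8%, up to three species, nothing missing and 3,000 trials per cell, null rejection for treatment only v full set was 5.3% v 4.9% with no covariate effect, 4.2% v 5.3% with moderate effects and 3.6% v 5.1% with strong ones. At a set 10-point difference the two models disagreed on p ≤ 0.05 in about 5% to 6% of trials.

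**The case against.** The departure is not hidden. The Preface announces updated analyses, Section 6.7 states that sites are pooled, the treatment-only model is written out and coded, and Protocol 11.4 leaves details to the SAP. A simpler model is defensible at 48 subjects: the full protocol set enlarges the true SD and, with 20% missing, has type I error of 5.5% to 5.8%. A model with pyelonephritis alone is not the protocol model either, omits the site stratum, and would be fixed after enrolment closed in an open-label trial. Nothing in the documents shows that pyelonephritis is prognostic. Outside the strongest assumed scenario, adding it moves type I error by at most 0.3 points, close to simulation noise. The work also exceeds one model term, because Tables 20 and 21 print percentages per arm beside the difference and Tables 24 and 25 are unadjusted grids.

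Much of this stands. The effect is small, the prognostic strength is assumed, and the full set should not be primary. It does not remove the point. No passage says that pyelonephritis and species count left the analysis model, and a written-out model does not tell the reader that it departs from the protocol. Pyelonephritis is both a stratum and a covariate the protocol already named, so adding it moves back towards the protocol. Table 15 shows cUTI type by arm and Table 26 gives complete-case differences by cUTI type for subgroups above 10 subjects; both could reveal an imbalance, but neither adjusts for it.

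**Conclusion.** The point holds. The Protocol 11.4 covariates are absent from every SAP efficacy model, no covariate-adjusted efficacy estimate remains, and Section 12 is silent on it. That conclusion rests on the texts alone.

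The numerical consequence rests on assumed stratum effects and is modest. The treatment-only estimate is unbiased. With nothing missing, its SE is 0% to 4% too large and type I error lies between 4.3% and 5.2%. If the strata are not prognostic, nothing is lost. SAP Section 5 already reports 12% power and warns against superiority conclusions, so the gain is a better-sized interval and a documented departure. The change should be made, but the trial's validity does not depend on it.

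**What to change.** 1. Add the pyelonephritis indicator to the Step 2 models at TOC and EOT (8.1.1, 8.2.1 and the 8.4.1 code) and to the 8.2.2 complete-case model. Report the adjusted risk difference with its 95% CI.
2. Report the full Protocol 11.4 set as a named sensitivity analysis beside Table 21, with any pooling of sparse sites fixed before database lock. Do not make it primary at 48 subjects.
3. In Section 12, state which covariates left the analysis model, that they remain in the imputation model, and why. This entry is needed even if the sponsor keeps treatment only as primary; in that case at least one adjusted estimate should still be reported.
4. Footnote Tables 20 and 21 to explain that raw percentages need not subtract to the adjusted difference. Align the Step 3 decision wording, and label Tables 24 and 25 as unadjusted.

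**Cost.** All variables are already collected and listed in 8.4.1. With complete data, pyelonephritis takes residual degrees of freedom from 46 to 45. If it is not prognostic, simulated power falls from 11.9% to 11.5% at a 10-point difference and from 64.7% to 63.8% at 30 points. The full set, as sensitivity only, uses up to 4 + 1 + 2 = 7 degrees of freedom for site, pyelonephritis and the species levels of Table 19.
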